All identifiable participant information will be stored in a locked filing cabinet in the Co-PI's office ([name]), room 7017 on the TWU-Houston Campus. All other collection procedures will utilize a subject ID. The identifiable information (consent forms, medical records, ambulatory blood pressure monitor patient care forms) will be stored in a separate folder and apart from all other non-identifiable data folders. The subject codebook will be on a password-protected computer in the Co-PI's office ([name]).

*required

Electronic Transmission of Identifiable Private Information

Will the identifiable private information be transmitted electronically? (This includes, but is not limited to downloading, emailing, transferring from cloud storage to computer/hard drive/flash drive, and/or video conferencing.)

Yes

✓ No

*required

Identifiable Private Information Destruction Timeline

Will the documents containing Identifiable Private Information be destroyed?

✓ Yes

*required

Timeline for the Destruction

Provide a time frame for when the documents containing identifiable private information will be destroyed. (e.g., 5 years after the completion of the study.) 3 years after completion of the study

*required

Method(s) of Destruction

Identify specific ways that the documents containing identifiable private information will be destroyed at the end of this period of time.

The signed consent forms, medical records, and ambulatory blood pressure monitor patient care forms will be removed from locked filing cabinets and shredded. Digital data corresponding to the subject codebook will be erased from all servers.

No

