Participants who meet the inclusion/exclusion criteria for participation (as determined by Qualtrics pre-screening survey or pre-screening phone or Zoom call) will be asked to attend an in-person screening and consent visit at TWU – Houston. During the in-person screening visit, participants will complete a questionnaire regarding demographic and medical history, as well as the PAR-Q. Participants will also be asked to provide a copy of their medical records confirming the diagnosis of hypertension with or without current medication use. In addition, we will measure height, weight, and seated resting BP, to ensure that they meet the inclusion criteria for BMI and BP, respectively. If they pass screening, participants will undergo written informed consent to be enrolled in the study. At the end of this screening and consent visit, each participant will be provided with a physical activity/sleep monitor (Fitbit) to wear for 7 days. This is to ensure participants meet the criteria for sedentary or inactive – defined as < 7,500 steps per day. In addition, this Fitbit monitor also objectively measures sleep duration and quality (further details below). Finally, each participant will also be provided with an Ambulatory Blood Pressure Monitor to wear for the next 2 days.

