Monitor (ABPM) (Oscar 2 ABP, Sun Tech Medical, Morrisville, NC) to wear for 48 h prior to and then again for 48 h during the final week of the lifestyle intervention. ABPM is a non-invasive, fully automated technique where BP is measured and recorded frequently over an extended period of time - typically 24 h. The major advantages of ABPM include the collection of multiple BP measurements to provide more comprehensive information on BP (mean 24-h BP readings) and ability to measure both daytime and nocturnal BP in a more natural setting. Over the last few decades, multiple studies have shown that BP measured by ABPM has a stronger association with clinical CVD outcomes compared with standard office-based BP measurements. For this study, each ABPM will be programmed to record BP measurements every 30 min during waking hours and sleep. We will NOT use an app for this device, we will initialize (set-up) the device by entering the participant's non-identifiable study ID onto the device. The ABPM only records blood pressure, heart rate, and time of each measurement. When the ABPM is returned to us we connect it to the PC via a USB and download the blood pressure, heart rate, and time of measurement data from the device. Each participant will receive a verbal explanation and demonstration regarding the process of ABPM and written instructions regarding frequency of inflations and deflations, how to deflate manually, and how to keep the monitor attached at night. Participants will also be provided with an activity diary to complete while wearing the ABPM, which includes hours of sleep, time at work, time at leisure activities, and periods of driving. Times used to define daytime and nighttime will be determined by using self-report (activity diary sleep times) and actigraphy (Fitbit). This will allow us to define the mean 24-h BP, daytime BP, and nocturnal BP. ABPM readings will be considered acceptable for data analysis purposes if ≥ 70% of planned readings are acquired. All ABPM devices must be returned to the study team immediately following completion of baseline and post-intervention testing.

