Physical Activity and Sleep: Habitual physical activity levels and sleep will be measured using a wrist-worn, physical activity and sleep monitor (Fitbit Inspire 3, Fitbit LLC, San Francisco, CA) for the duration of the study. The Fitbit Inspire 3 device uses motion sensors (Actigraphy) and heart rate to measure total steps and minutes of light, moderate, and vigorous physical activity. These measurement tools also allow it to measure total time in bed, total sleep time (sleep duration), and wake time after sleep onset. It also uses a proprietary sleep staging algorithm to derive sleep stage durations including light, deep, and rapid eye movement (REM) sleep. Prior studies indicate that Fitbit is a reliable alternative to polysomnography (the gold standard) for collecting objective sleep data.

We will use Fitbit's free, web-based application programming interface (API) to tailor the Fitbit to the specific needs of this study. Fitbit API allows us to created deidentified participant accounts using unique codes that are specific to the study - for example "Study Participant 001". These de-identified Fitbit accounts are also linked to unique, study-generated gmail accounts such [contact] and not a personal email account. This effectively removes any personal information (email, name, DOB, phone number) directly linked to the data collected during the study with Fitbit. At the first study visit, our team will show each participant how to download the Fitbit app to their mobile device/smartphone and then have them use the deidentified Fitbit account and study-generated Gmail account information provided to them to set up their account. Once their deidentified Fitbit account is setup we will send them a "push" to approve us to access the data, which is automatically downloaded to their app every time they open the app and "sync" it. We will only collect physical activity, heart rate, and sleep data from the Fitbit device for this study. Physical activity data includes steps taken and moderate-to-vigorous intensity physical activity minutes per day. Sleep data includes sleep duration and sleep quality indices (light, deep, REM, non-REM sleep). We only collect Fitbit data that directly impacts study outcomes. Once paticipant data is accessed we will download it as an Excel file for storage on a password-protected computer for later analysis.

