The form "MIND Study_Oscar 2 ABPM Device Patient Care Agreement Form" requests that the participant share their name and contact details (phone number and physical address) with us. The College of Health Sciences and Institute of Women's Health requested that we have participants complete this form as a deterrent for theft - these ambulatory blood pressure monitors cost ~\$3,000 each. We will keep this completed form in the same binder as other identifiable information (signed consent form and any copies of medical records) in locked cabinet in [name] office. It will always be separate from non-identifiable participant data.

No

Potential Risks and the Steps to Minimize the Risks

*required

List all the potential risks to the human subjects involved in this research. All risks must be identified and listed on the consent form (if applicable).

Please ONLY list the risks here. Descriptions and steps to minimize will be requested below.

Study risks include:

- Risk of an adverse cardiovascular event during exercise testing and exercise training
- Risk of increased muscular soreness and injury during exercise training
- Exposure to very low levels of radiation during body composition testing using the dual energy X-ray absorptiometry (DEXA)
- Discomfort, minor pain, bruising, swelling, anxiety, infection, light-headedness, or fainting during the blood draw
- Risk of sleep disruption due to wearing the ambulatory blood pressure monitor
- Risk of coercion
- Loss of participant time
- Loss of data to a third party
- Loss of participant confidentiality

As such we have outlined the strategies we will utilize to minimize each of these risks in the section below.

*required

Describe how each risk will be minimized.

Make sure all steps listed here match the steps listed in the consent form. Potential Risks

Potential physical risks to participants in this study will be minimized by using only trained research personnel in testing procedures. If you do not feel comfortable with testing procedures, the test will not be completed at that time.

In the instance that information indicates immediate action is needed, emergency personnel will be contacted. You may ask questions at any time during the study protocol.

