The risks of drawing blood from your arm include pain or discomfort, possible bruising and swelling, rarely an infection, and lightheadedness from the procedure. To reduce these risks only a trained phlebotomist will draw your blood. Only ~2 teaspoons of blood will be collected. Your arm will be cleaned with alcohol before the collection. Drinking water the morning of the blood draw is

encouraged to minimize the risk of bruising and improve blood flow. Only non-latex gloves will be used to minimize the risk of latex allergy.

Body composition will be measured using dual energy X-ray absorptiometry (DEXA). Very low levels of radiation are used, as such the researcher will obtain verbal acknowledgement from you stating that you are certain that you are not pregnant, nor planning to get pregnant. You will lie on a padded table for approximately 6 minutes while your body is scanned. A whole-body scan produces less than one-tenth of the radiation dose of a standard chest X-ray and less than one day's exposure to natural radiation. To minimize the risk of radiation exposure, only one DEXA scan will be performed. If a second DEXA scan is needed, you will provide additional consent. No more than two scans will be performed on one day.

You may experience disruptions in sleep while wearing the portal blood pressure monitor. To minimize this risk, we will provide troubleshooting tips to help avoid major sleep disturbances during your initial education session at the end of the baseline testing visit. In addition, you will only be required to wear the blood pressure monitor for 2 days at the beginning, and then again for 2 days at the end of the study.

You may experience increased shortness of breath, muscle tiredness, lightheadedness, and/or dizziness during exercise. There is a very minor risk of a heart attack or cardiac arrest happening during exercise. However, we will take all necessary precautions to further reduce your risk. All exercise testing and training will be supervised by a certified exercise training specialist and all research staff are CPR-certified. Your heart rate and blood pressure will be measured before, during, and after each training session for additional precautions. If we notice an irregular heart rate or blood pressure response during exercise, we will stop the training session immediately.

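### About two of the seven baseline Fitbit sleep nights are recorded under the ABPM cuff, and as written the tips for limiting its effect on sleep come after that first wear but before the second

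*Protocol*

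**What the plan says.** Aim 3 of the Protocol (Research Questions/Hypotheses/Objectives) hypothesises better sleep duration and quality. The Statistics section tests pre-post change within the single group with paired t-tests, two-sided at 0.05.

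The Study Design text under Research Procedures issues two devices at the end of the screening and consent visit. One is a "physical activity/sleep monitor (Fitbit) to wear for 7 days", and the text adds that "this Fitbit monitor also objectively measures sleep duration and quality". The other is the blood pressure monitor: "each participant will also be provided with an Ambulatory Blood Pressure Monitor to wear for the next 2 days". Both are collected about a week later at baseline testing, so this week is the only Fitbit sleep recorded before the intervention.

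Under Ambulatory Blood Pressure Monitoring, "each ABPM will be programmed to record BP measurements every 30 min during waking hours and sleep". The same paragraph schedules a second 48 h wear in the final intervention week. The Physical Activity and Sleep paragraph has the Fitbit worn throughout ("Fitbit Inspire 3, Fitbit LLC, San Francisco, CA) for the duration of the study").

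The section on risks and their minimisation lists "Risk of sleep disruption due to wearing the ambulatory blood pressure monitor". Its mitigation is troubleshooting advice on sleep, to be given "during your initial education session at the end of the baseline testing visit".

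**The concern.** Sleep is both an outcome and something that another study measurement disturbs. The baseline week, which supplies one half of every paired difference, has about two nights with a cuff inflating every half hour. If the follow-up value has a different share of such nights, or if the cuff disturbs sleep less the second time, part of the measured sleep change comes from the monitor. With no control arm, nothing in the design separates that part from an intervention effect.

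The stated timing of the advice adds a second asymmetry. By the baseline testing visit the first wear is over and the device is being handed back. Advice given when that visit closes can help only with the second wear.

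**Working it through.** The Protocol gives no bias, power or sample-size figure for sleep, so there is nothing of its own to reproduce. The check is a count of nights and a simple formula.

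**Inputs from the Protocol**
- Baseline Fitbit window: 7 days from the screening and consent visit (Study Design).
- Baseline ABPM wear: the first 2 days of that week, about 2 nights (Study Design).
- Follow-up ABPM wear: 48 h in the final intervention week, about 2 nights (Ambulatory Blood Pressure Monitoring; repeated in the risk section).
- Intervention length: 4 weeks, 28 nights.
- Target completers: at least 9 (Subject Enrollment).

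**Assumptions, not in the Protocol**
- Sleep lost per ABPM night: 15, 30 or 60 min.
- SD of the paired sleep change: 30 to 60 min.
- The nights that make up the follow-up value: several windows are tried.

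**Formula.** Let s0 and s1 be the shares of ABPM nights at baseline and follow-up, and L0 and L1 the minutes lost per ABPM night at each wear. The artefact in the mean change (positive = apparent gain) is

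artefact = s0 × L0 − s1 × L1

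with s0 = 2/7 = 0.286. If L0 = L1 = L, this becomes (2/7 − s1) × L.

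**Step 1: equal disturbance at both wears**

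| Follow-up window | s1 | 2/7 − s1 | L = 15 | L = 30 | L = 60 |
|---|---|---|---|---|---|
| Final 7 intervention nights, both ABPM nights inside | 2/7 | 0 | 0 | 0 | 0 |
| All 28 intervention nights | 2/28 | +0.214 | +3.2 | +6.4 | +12.9 |
| Nights with no ABPM | 0 | +0.286 | +4.3 | +8.6 | +17.1 |
| Last 4 nights, including both ABPM nights | 2/4 | −0.214 | −3.2 | −6.4 | −12.9 |

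At L = 30 the range over these windows is −6.4 to +8.6 min.

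**Step 2: unequal disturbance, equal shares.** With s0 = s1 = 2/7 the artefact is (2/7) × (L0 − L1). Each 10 min by which the second wear is less disturbing leaves 10 × 2/7 = 2.9 min of apparent gain. The Protocol gives no basis for a value of L0 − L1.

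**Step 3: order of events as written**
1. Screening and consent visit: ABPM and Fitbit issued (Study Design).
2. Next 2 days: first ABPM wear.
3. About a week after screening: baseline testing, ABPM retrieved (Study Design).
4. Close of baseline testing: sleep tips given (risk section).
5. Final intervention week: second ABPM wear.

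The tips fall between the two wears, so equality of L0 and L1 is not secured by the text.

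**Step 4: effect on the test.** For the largest positive case in step 1 and n = 9, the noncentral t distribution gives these false-positive rates for the nominal 0.05 test:

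| L (min) | Artefact (min) | SD of change 30 | SD of change 60 |
|---|---|---|---|
| 15 | 4.3 | 0.07 | 0.05 |
| 30 | 8.6 | 0.12 | 0.07 |
| 60 | 17.1 | 0.33 | 0.12 |

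**Step 5: after excluding ABPM nights.** Then s0 = s1 = 0 and the artefact is 0 whatever L0 and L1 are, provided the cuff does not affect sleep on later nights.

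**The case against.** A reader might infer that the baseline contamination will show up as a spurious sleep improvement. The documents do not support that. The ABPM is worn for 48 h at both ends and the Fitbit throughout, so the natural comparison of seven baseline nights with the final seven intervention nights has 2/7 ABPM nights on each side and the effect cancels. A short window around the second wear would even bias against the intervention. This part of the objection stands, and no direction is claimed here.

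Which nights form the follow-up value is ordinary content for a statistical analysis plan, which is not shown, so its absence from the Protocol is no fault. That stands too. Cancellation is still not automatic. Outcomes are reassessed 2 to 4 days after the intervention ends, so the seven nights before the final visit include only part of the final week and could hold 0, 1 or 2 ABPM nights.

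On the tips, the other side can say that participants get a verbal explanation, a demonstration and written instructions on wearing the monitor, including overnight, presumably when it is issued. The Protocol also labels visits loosely elsewhere: it places consent at the screening visit, at the initial study visit and at the baseline study visit. The risk text may therefore be a slip in the visit label. That is plausible, and it is why no figure is put on the effect of the tips. It does not remove the mismatch between the risk section and Study Design.

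The reach is also limited. Sleep is one item of Aim 3 in a small pilot, and the PSQI recalls 30 days, of which two ABPM nights are 2/30, about 7%.

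**Conclusion.** The point holds in a modest form. About 2 of the only 7 baseline Fitbit nights are recorded under a disturbance that the Protocol acknowledges. With matching windows and equal disturbance at both wears there is no net bias. Otherwise the bias is the difference in ABPM shares times the loss per night and can take either sign: about −6 to +9 min for an assumed 30 min loss over the windows examined, in proportion for other losses. Separately, the stated timing of the sleep tips means that the two wears are not under the same conditions. This could lessen disturbance at follow-up only, by an amount the documents do not let one estimate.

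The minutes rest on an assumed loss per night, and the false-positive rates also on an assumed SD. The count of nights and the order of events come directly from the text. This is a cheap improvement to a secondary outcome, not a threat to the trial.

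**What to change.** 1. Exclude every night on which the ABPM is worn from both the baseline and the follow-up Fitbit sleep averages, and use matching windows. The ABPM stores the time of each reading, so these nights can be identified from data already collected. About 5 nights remain at baseline, to be set against the matching non-ABPM nights of the final week.
2. Reconcile the risk section with Study Design so that the sleep tips are given when the device is first issued, at the screening and consent visit. Both wears then take place under the same instructions.

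The cost is one analysis filter, one change of wording, and two fewer nights in each average, which makes each participant's mean somewhat less precise. No new data or visits are needed.

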Approximately one week later, participants will return to our research lab at TWU Houston to undergo baseline testing. At this time, the research team will retrieve the ambulatory blood pressure monitor and Fitbit monitor from the participant to ensure compliance and eligibility, respectively. **We require a minimum of 70% of ambulatory blood pressure monitor recordings over a 24-hour period and an average daily step count of < 7,500 steps per day during the initial week of monitoring to qualify for the study.**All testing visits will be completed early in the morning following an overnight fast - water is permitted. Participants will be instructed not to consume any caffeine or alcohol, take any dietary supplements, or conduct vigorous exercise 24 hours prior to this visit. Thereafter, participants will undergo numerous physiological testing including seated resting BP, assessment of vascular function, anthropometry, venous blood draw, and maximal exercise testing to measure maximal oxygen uptake (VO2max). In addition, we will have participants complete surveys on quality of life and sleep quality, and current dietary intake. Following the completion of baseline testing, all participants will undergo a 4-week lifestyle intervention consisting of the MIND diet and supervised exercise training - HIIT. All study outcomes will be reassessed 48 to 96 h after the intervention is completed. All outcome assessments and exercise training will take place in the 10th floor research wing at TWU - Houston. The return of ambulatory blood pressure monitors is required after baseline and post-intervention testing. The Fitbit monitors must be returned to the study team immediately upon study completion at the final testing visit.

Procedures & Methodology

Private rooms are available for the PI to obtain informed written consent and collect other health-related data (medical history questionnaire and list of medications). All exercise testing and training for this study will take place in the Cardio Lab (Room 10131) located on the 10th floor research wing at TWU – Houston. The following assessments will be performed at baseline and post-intervention (in this order):

Ambulatory Blood Pressure Monitoring: Each participant will be given an Ambulatory Blood Pressure

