Supervised Exercise Training: All subjects will complete 4 weeks of supervised exercise training in the Cardio Lab (Room 10131) at TWU – Houston. The supervised exercise training sessions will take place on 3 days per week and consist of high-intensity aerobic interval training (HIIT) on a cycle ergometer. Each HIIT session will be 30 minutes and consist of a 5-min warm-up at 50-60% HRmax followed by ten 1-min vigorous intervals at 90-95% HRmax separated by 1-min periods of active recovery at a low-intensity (30 to 50W), with a 5-min cool-down at 50-60% of HRmax. Heart rate will be continuously measured with Polar HR monitors and recorded to ensure adherence to prescribed exercise intensities. To ensure patient safety and appropriate aerobic endurance progression, high-intensity intervals will be set at 80 to 85% HRmax during week 1 and gradually increased up to 90 to 95% HRmax by week 3 of the study. A summary table of the supervised exercise training protocol is also included as an attachment for easy viewing. Participants will be advised to maintain their usual physical activity outside of the exercise sessions and this will be confirmed with a wrist-worn physical activity monitor for the duration of the study.

Dietary Intervention: Participants will meet with a registered dietitian (Study PI or Co-PI) and receive diet education on how to adopt and adhere to a MIND diet. The MIND (Mediterranean-DASH Intervention for Neurodegenerative Delay) diet has emerged as a promising intervention, yielding favorable improvements in BP and other CVD markers. The MIND diet shares similarities with both the Mediterranean and DASH diets by prioritizing natural, plant-based foods while restricting the intake of animal products and foods high in saturated fat. However, it distinguishes itself through its unique emphasis on the inclusion of

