berries and green leafy vegetables. For adoption of the MIND diet, participants will be instructed to consume fatty fish at least twice per week (6-10 oz.), 5 servings of berries weekly (2 ½ cups), 5 servings of nuts weekly (5 oz.), one serving of leafy greens daily (1 cup raw, ½ cup cooked), and at least 2 tablespoons of extra virgin olive oil daily (used in cooking or dressings). In addition, they will be instructed to limit red and processed meats to no more than 1 serving per week (3-5 oz.), fast or fried foods (including potato chips) no more than once per week, and sweets no more than 3 times per week. The research team will provide participants with a stipend (\$25 gift card each week) for grocery shopping, a daily 30g whey protein supplement, 48 oz of extra-virgin olive oil, and packaged mixed nuts to help with compliance. To track dietary compliance, participants will be provided with a dietary tracker, which includes the foods to incorporate and limit, and instructed to complete and return the tracker each week.

Statistics

All data will be analyzed using IBM SPSS software (Version 25, IBM, Armonk, NY). Data will be explored for departures from normality with the Shapiro-Wilk test. Paired T-tests will be used to assess changes (pre-post) in main outcome measures following the intervention within-group. In the event that data are observed to violate parametric assumptions, group comparisons will be made with Wilcoxon signed-rank tests where appropriate. All statistical tests will be two-sided with a critical alpha level of 0.05 indicating statistical significance.

*required

Is video recording a part of this study?

Yes

✓ No

*required

[figure not shown]
Is audio recording a part of the study?

Yes

✓ No

*required

Is internet/email a part of the study?

Each subject will come to the TWU Houston Campus for a total of 15 study visits. The initial screening and consent visit will take 1 hour to complete. The baseline and post-intervention testing visits will each take

~2.5 hours. The exercise training visits (12 total) will each take ~45 minutes (9 hours total for exercise training during study). **Total maximum study time commitment is 15 hours, which does not include travel to and from TWU.**

*required

Subject Data, Specimens, and Records

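### The second ambulatory BP recording is timed two ways, in the final training week and 48 to 96 h after the intervention, and the protocol text does not fix its distance from the HIIT sessions

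*Protocol*

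**What the plan says.** - **General rule (Study Design):** "All study outcomes will be reassessed 48 to 96 h after the intervention is completed".
- **List of assessments (Procedures & Methodology):** "The following assessments will be performed at baseline and post-intervention (in this order". Ambulatory Blood Pressure Monitoring is the first item.
- **Device rule (Ambulatory Blood Pressure Monitoring):** the monitor is issued to "wear for 48 h prior to and then again for 48 h during the final week of the lifestyle intervention".
- **Training (Supervised Exercise Training):** "The supervised exercise training sessions will take place on 3 days per week", for all 4 weeks, with interval intensity at its highest from week 3.
- **Baseline recording (Study Design, screening visit):** "Finally, each participant will also be provided with an Ambulatory Blood Pressure Monitor to wear for the next 2 days". This is before any study exercise.
- **Visits (time-commitment paragraph):** "Each subject will come to the TWU Houston Campus for a total of 15 study visits". These are one screening, two testing and twelve training visits.
- **Analysis (Statistics):** "Paired T-tests will be used to assess changes (pre-post) in main outcome measures following the intervention within-group".

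The risk section tells participants only that the second recording takes place over two days at the end of the study, which fits either timing. An ABPM protocol is listed under Study Instruments but is not shown.

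**The concern.** One rule puts the second recording after the intervention and the other puts it inside the intervention. Staff following either rule would be following the protocol, yet they would collect different measurements.

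The final week holds three HIIT sessions, and the text shown does not say on which days the monitor is worn relative to them. One participant's post recording may span a session and the hours after it, while another's may not. The baseline recording contains no study exercise at all. Ambulatory BP is one of the two BP measures available for Aim 2, and the protocol itself describes it as more strongly related to cardiovascular outcomes than office readings. The analysis is a pre-post change in a single group, so no control arm can separate the after-effect of a recent session from the effect of the programme. The timing of wear cannot be corrected once the data are collected.

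**Working it through.** The protocol gives no figure to reproduce here. The check compares the two rules on one time line.

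**Visit count.** 1 screening + 2 testing + 12 training = 15. No visit is left over for issuing or collecting a monitor.

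**Overlap if completion means the end of the 4-week programme.** Final-week wear ends by the close of week 4. The general window opens 48 h later. Overlap = 0 h.

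**Overlap if completion means the last HIIT session.** Assumptions: week 4 runs from Monday 00:00 to Sunday 24:00, and 30-minute sessions start at 07:00 or 18:00, so they end at 07:30 or 18:30. The general window runs from 48 to 96 h after the last session. The overlap is the part of it before Sunday 24:00.

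| Last session | Window opens | Overlap with week 4 |
|---|---|---|
| Wed | Fri 07:30 or 18:30 | 48 h (window closes Sun 07:30 or 18:30) |
| Thu | Sat 07:30 or 18:30 | 40.5 or 29.5 h |
| Fri | Sun 07:30 or 18:30 | 16.5 or 5.5 h |
| Sat | Mon 07:30 or 18:30 | 0 h |

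A full 48 h recording can satisfy both rules only in the first row. With three sessions on separate days from Monday to Saturday, that means Mon/Tue/Wed.

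**Exposure to HIIT under final-week wear (illustration).** Take every half-hourly start of a 48 h window inside week 4: (168 − 48) × 2 + 1 = 241 windows.

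- Mon/Wed/Fri at 07:00: a window contains a session if it starts no later than hour 103 (Friday 07:00), which gives 207/241 = 86%. At 18:00 the limit is hour 114, which gives 229/241 = 95%.
- Mon/Tue/Wed: the limits are hours 55 and 66, which give 111/241 = 46% and 133/241 = 55%.
- Tue/Thu/Sat: every window contains a session, 100%.

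**Spread between single windows (illustration).** A 48 h recording at one reading per 30 minutes has 96 planned readings. Take Mon/Tue/Wed sessions ending at 07:30. Wear from Monday 07:30 to Wednesday 07:30 puts all readings within 24 h after a session. Wear from Thursday 07:30 to Saturday 07:30 puts none there.

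Session days and times are assumptions. These figures show what the text permits and do not estimate what this trial will do.

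**Does post-intervention wear fit the schedule?** Suppose the last session ends at 16:30 and the testing visit is at 08:00. The visits that fall inside 48 to 96 h are then at 63.5 h or 87.5 h. Wear that starts at 48 h gives only 63.5 − 48 = 15.5 h or 87.5 − 48 = 39.5 h before the visit. Under this option the start of wear must therefore be stated.

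**The case against.** The strongest reply is that context already settles the matter. Study Design goes on to place all outcome assessments in the research wing, which cannot describe a 48 h recording in daily life. Nor can the 48 to 96 h rule literally cover the Fitbit data, which are collected throughout the study. Read this way, the general rule describes the laboratory visit and the device paragraph governs the monitor. Final-week wear also mirrors baseline, where the monitor is worn before the testing visit and collected at it, and it fits the 15 visits. This makes the device paragraph the likelier working rule. It does not remove the conflict, because the general rule covers every outcome without exception and the device heads its list. It also leaves open where in the week the 48 h fall.

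A second reply is that the monitor can be handed out only at a training visit. If wear starts at once, the first 24 h always follow a session, which is 48 of 96 readings, and participants would differ less than the full range above. That is plausible, but the protocol text does not say it. The unseen ABPM protocol may fix the wear days, although it cannot make the two protocol passages agree.

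Three stronger readings are tempting and are not supported:

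- A reader might infer that the two timings can never overlap. That depends on what completion means, which the protocol does not define.
- A reader might see a breach of the rule not to "or conduct vigorous exercise 24 hours prior to this visit". That rule is tied to the fasted testing visit and does not extend to the ambulatory recording.
- A reader might conclude that the BP change will be biased by a known amount or in a known direction. The documents give no basis for either. Recording during an ordinary training week is also a defensible choice, and later wear is not automatically free of recent exercise.

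**Conclusion.** The conflict stands and should be fixed before post-intervention recordings begin. As written, the protocol permits two different post-intervention ambulatory BP measurements. They share 0 h if completion is the end of week 4, and between 0 and 48 h if it is the last HIIT session, under the assumed calendar week and session times. Under the likelier rule, final-week wear, the text shown leaves the distance from HIIT open. The paired change for Aim 2 can then mix recent-session and programme effects to a degree that may differ between participants. No effect in mmHg is claimed. Confidence is high that the passages conflict. It is lower that the wear days are truly unfixed, because the ABPM protocol is not shown.

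**What to change.** Reconcile Study Design, the Ambulatory Blood Pressure Monitoring paragraph and the attached ABPM protocol so that they give one post-intervention wear window. Define when the intervention is completed. Fix the start of wear relative to the last HIIT session, the same for every participant. The sponsor can choose either option:

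1. **Final-week wear.** Name ambulatory BP as an exception to the 48 to 96 h rule, fix the wear days relative to the sessions, and record session times. A sensitivity analysis without readings taken during or soon after a session is optional. All readings should stay in the main analysis.
2. **Post-intervention wear.** State when wear starts, so that the full 48 h fits before the post-testing visit at which the monitor is returned.

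The cost is protocol wording and slightly less scheduling freedom. Under option 2 the monitor would have to be handed over at the last training visit, because the 15 visits include no other, and the testing visit may have to fall late in its window.
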